Study title: Lumen apposing metal stents vs lumen apposing metal stent plus double pigtail stent for endoscopic drainage of pancreatic fluid collections: a randomized controlled trial

Principal Investigator: [name] MPH

Background:

Pancreatic fluid collections (PFC) develop as a consequence of acute pancreatitis. Chronic PFCs can cause significant patient morbidity and need for hospitalization including: pain resulting in disability and requirement for chronic pharmacologic analgesia; gastric outlet obstruction resulting in inability to tolerate oral intake, weight loss, and nutritional compromise; obstructive jaundice; hemorrhage; and infection.

Interventional approaches for management of symptomatic PFCs include endoscopic or surgical drainage. Endoscopic drainage has emerged as the preferred first line-intervention due to the ability of endoscopic drainage to offer effective therapy in a minimally invasive fashion, with comparable efficacy, lower cost, and shorter length of hospital stay compared to surgical drainage [1].

Standard technique for endoscopic drainage has consisted of endoscopic ultrasound (EUS) for visualization of PFC, which are typically in a perigastric or periduodenal location, followed by EUS-guided transgastric or transduodenal needle access to the collection, creation of a cystotomy tract, and finally placement of a transmural stent which facilitates drainage of PFC contents into the gastrointestinal lumen.

At the time of initial development and clinical application, this technique required use of plastic or metal bile duct stents for cystgastrostomy/cystduodenostomy. More recently however, a dedicated lumen apposing metal stent (LAMS) (Axios, Boston Scientific) (Figure 1) has been granted U.S. Food and Drug Administration approval for transmural drainage of pancreatic pseudocysts (PP).

The first clinical use of an Axios stent at Vanderbilt for treatment of a PFC was in March 2015. Vanderbilt University Medical Center (VUMC) was the first and to date remains the only medical center in Tennessee where the Axios stent is in clinical use. Since March 2015, Axios stents have been placed in more than 25 patients at VUMC for management of PFCs, with a favorable efficacy and safety profile. VUMC clinical experience with the Axios stent through November 2015 was included in an international multicenter study for management of PFCs in 192 patients, which reported a 98.4% technical success rate, 92.6% clinical success rate, and a low adverse event rate [2].

In many instances, however, PFCs may contain considerable solid debris indicating the presence of walled off necrosis (WON) rather than simple PP. Such solid debris may occlude the lumen of LAMS, resulting in incomplete drainage, persistent symptoms, infection, and hospitalization. In cases of WON, passage of a flexible endoscope across the cystotomy tract may be necessary for endoscopic necrosectomy and mechanical debridement of pancreatic necrosis. Published data indicate that more than half of patients will require such additional endoscopic interventions for debridement of necrosis following LAMS placement [3, 4].

Clinical experience suggests that placement of an overlapping double pigtail plastic stent through the lumen of the LAMS will prevent stent occlusion, enable optimal drainage following LAMS placement,

Study title: Lumen apposing metal stents vs lumen apposing metal stent plus double pigtail stent for endoscopic drainage of pancreatic fluid collections: a randomized controlled trial

Principal Investigator: [name] MPH

and minimize the need for endoscopic reintervention (Figure 2). Controlled data to support this approach are lacking. The objective of this study is to randomize patients undergoing endoscopic drainage for PFCs containing solid debris to placement of either LAMS alone vs LAMS plus an overlapping double pigtail stent.

Study hypothesis and objectives:

The study hypothesis is that placement of LAMS plus an overlapping double pigtail stent for endoscopic transmural drainage of PFCs with solid debris will result in improved drainage and require fewer endoscopic interventions compared to placement of LAMS alone.

Study endpoints/outcome measures:

Primary endpoint:

Greater than 50% decrease in size of PFC (in mm), compared to pre-intervention size (in mm), on cross-sectional computed tomography (CT) imaging at 30 days following stent placement. This was selected as the primary outcome in order to maintain consistency with the primary outcomes of a prior multicenter study of LAMS placement for PFCs [5].

Secondary endpoints:

- 1) Clinical success rate for drainage of PFC, defined as complete resolution of PFC on follow-up computed tomography (CT) imaging and stent removal within 3 months;
- 2) Number of endoscopic interventions required for resolution of PFC prior to stent removal;
- 3) Need for hospital readmission following initial endoscopic intervention and prior to resolution of PFC/stent removal;
- 4) Need for surgical or percutaneous radiologic intervention for PFC following initial endoscopy intervention
- 5) Need for early (<30 days) endoscopic reintervention

Methods:

Adult patients with symptomatic pancreatic fluid collections who are scheduled to undergo EUS-guided drainage of PFCs with LAMS placement will be eligible for study participation. The initial portion of this procedure consists of diagnostic EUS for imaging and assessment of the PFC. This EUS examination is able to distinguish the relative liquid and solid components of PFCs, detail which may not be evident by CT imaging. Adult patients with PFCs consisting of >30% solid component as assessed at the time of EUS will be eligible for randomization. This threshold was selected as the enrollment criteria in order to select patients with a significant solid necrotic component to the lesion, as prior study of patients undergoing LAMS placement for drainage of PFCs have used >70% fluid content as the definition for a PFC with predominantly liquid contents [5].

Study title: Lumen apposing metal stents vs lumen apposing metal stent plus double pigtail stent for endoscopic drainage of pancreatic fluid collections: a randomized controlled trial

Principal Investigator: [name] MPH

Allocation to study arm will be determined by the contents of sealed envelope. Subjects randomized to LAMS alone will undergo EUS-guided transmural placement of an Axios stent with a 15 mm luminal diameter. The choice of transgastric or transduodenal LAMS placement will be at the discretion of the endoscopist and contingent upon PFC location and window relative to the EUS transducer. Subjects randomized to LAMS plus double pigtail stent will undergo EUS-guided transmural placement of a single Axios stent with a 15 mm luminal diameter; following this, wire access across the stent lumen will be achieved using a 0.035 inch hydrophilic guidewire, and a double pigtail plastic biliary stent (6 French, 7 French, or 10 French at the discretion of the endoscopist) will be deployed over the wire. The use of fluoroscopy for stent deployment will be at the discretion of the endoscopist.

Power calculation and statistical analysis plan:

The planned study is a prospective randomized study in which subjects undergoing intervention A (LAMS alone) vs subjects undergoing intervention B (LAMS plus double pigtail stent) will be randomized in 1:1 fashion. If the failure rate (<50% decrease in size of collection on 30 day imaging) for subjects undergoing intervention A is 50% and the failure rate for subjects undergoing intervention B is 20%, then 38 subjects will need to be enrolled in each intervention arm in order to reject the null hypothesis that the failure rates for intervention A and B are equal with 80% power at an alpha (Type I error) level of 0.05. Statistical analysis of this outcome will be performed using Chi square testing.

Study timeline:

In order to accrue 76 subjects (38 in each arm), and assuming a 20% drop-out rate, 101 total subjects would need to be enrolled in this study. Given the volume of procedures performed for EUS-guided drainage of PFCs at VUMC, we anticipate that this study would be able to achieve target prospective enrollment during a period of 36 months.

Study funding:

This study will be supported by internal funding. The study will not be supported or funded by industry, and the collection, analysis, interpretation, and publication of data will be independent of industry.

Disclosures:

[name] has received consulting fees and speaking honoraria from Boston Scientific.

References:

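### The primary endpoint is scored only on day-30 CT size, so a collection drained surgically or percutaneously before then can count as a stent success, and a death before the CT has no outcome

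*Combined protocol and SAP*

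**What the plan says.** Under Study endpoints/outcome measures, the primary endpoint is "Greater than 50% decrease in size of PFC (in mm), compared to pre-intervention size (in mm"), assessed "on cross-sectional computed tomography (CT) imaging at 30 days following stent placement". The reason given is "This was selected as the primary outcome in order to maintain consistency with the primary outcomes of a prior multicenter study" of LAMS placement.

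The Power calculation and statistical analysis plan section uses the same single criterion from the failure side: "If the failure rate (<50% decrease in size of collection on 30 day imaging) for subjects undergoing intervention A is 50" per cent, against 20% for LAMS plus pigtail. It names a chi-square test. It gives no analysis set, no rule for a missing CT and no rule for events before the CT.

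Secondary endpoint 4 is "Need for surgical or percutaneous radiologic intervention for PFC following initial endoscopy intervention". It has no day-30 window and no link to the primary endpoint. Secondary endpoints 2 and 5 cover the number of endoscopic interventions and early endoscopic reintervention. The text does not mention death. The only provision for patients without an outcome is in Study timeline: "assuming a 20% drop-out rate, 101 total subjects would need to be enrolled in this study".

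**The concern.** The hypothesis is that adding the pigtail "will result in improved drainage and require fewer endoscopic interventions compared to placement of LAMS alone". The primary endpoint should therefore separate collections that drained under the assigned stent strategy from those that did not. Surgical or percutaneous drainage within the first 30 days would usually mean that the strategy had not been enough. It also shrinks the collection, so it removes the evidence of failure from the CT that decides the outcome.

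If such rescue is more common with LAMS alone, some of that arm's failures become successes and the comparison is pulled toward no difference. If it is more common with the pigtail, the benefit of the pigtail is exaggerated.

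Death is a separate gap. A patient who dies before the CT has no size measurement, so whether that patient is dropped or scored would be decided after the event.

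**Working it through.** **Inputs from the plan.** Failure 50% v 20%, 80% power, alpha 0.05 (taken as two-sided), 38 per arm, chi-square test. **Not in the plan:** any rescue or death rate. All such figures below are assumptions.

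**1. The plan's own figure.** Pooled-variance formula: n = [1.96·√(2·0.35·0.65) + 0.8416·√(0.25 + 0.16)]² / 0.30² = 38.5, so 39 per arm. The arcsine formula gives 37.9, so 38. Exact power of the uncorrected chi-square test at 38 per arm is 80.0%. The stated 38 reproduces.

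**2. How the text classifies each case.**

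| Course before day 30 | Day-30 CT | Score under the text |
|---|---|---|
| No rescue | >50% smaller | Success |
| No rescue | <50% smaller | Failure |
| Surgical or percutaneous drainage | >50% smaller | Success |
| Death before CT | None | Neither |

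**3. Illustration: rescue in the LAMS-alone arm only.** With a and b failures in two arms of n, X² = 2n(a−b)² / [(a+b)(2n−a−b)]. At n = 38 the planned rates give 19 v 8 (8/38 = 21%).

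| LAMS-alone failures rescored | Failures | X² | p | Difference (points) |
|---|---|---|---|---|
| 0 | 19 v 8 | 76·121/(27·49) = 6.95 | 0.008 | 28.9 |
| 3 | 16 v 8 | 76·64/(24·52) = 3.90 | 0.048 | 21.1 |
| 4 | 15 v 8 | 76·49/(23·53) = 3.06 | 0.080 | 18.4 |

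At 50 per arm (about half of 101, as if every enrolled patient had an outcome), 25 v 10 gives p=0.002. Rescoring six (19 v 10) gives 0.047, and seven (18 v 10) gives 0.075, with the difference falling from 30 to 16 points.

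**4. Rescue in both arms, 38 per arm.** Equal numbers leave the difference unchanged and do not raise p: one each (18 v 7) gives 0.007, four each (15 v 4) gives 0.004. Unequal numbers do: four v one rescued (15 v 7) gives 0.043, five v one (14 v 7) gives 0.073.

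**5. Rescue in the pigtail arm only.** Rescoring three pigtail failures (19 v 5) gives X² = 76·196/(24·52) = 11.94, p<0.001, and a difference of 36.8 points instead of 28.9.

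**6. Cost of counting deaths as failures.** If a share d dies in each arm and the survivors fail at 50% and 20%, the rates become d + (1−d)·0.5 and d + (1−d)·0.2.

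| Assumed d | Failure rates | Exact power, 38 per arm |
|---|---|---|
| 0 | 50.0% v 20.0% | 80% |
| 2% | 51.0% v 21.6% | 77% |
| 5% | 52.5% v 24.0% | 73% |
| 10% | 55.0% v 28.0% | 67% |

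**The case against.** The strongest defence is that this is a choice of estimand. CT size is objective, it was chosen for consistency with a prior study, and scoring it whatever happened earlier, with rescue reported separately, is legitimate. This stands in part: it explains why size was chosen. But the plan does not say that size is to be scored regardless of rescue, that reading still leaves deaths unclassified, and it fits poorly with a hypothesis about drainage by the stent strategy.

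The illustration also needs a fair amount of rescue. At 38 per arm, losing significance takes four of 19 LAMS-alone failures (21%) rescued surgically or percutaneously within 30 days, all more than 50% smaller on CT, and none rescued in the other arm. At 50 per arm it takes seven of 25 (28%). Nothing in the documents shows that rescue is that frequent. This stands, and it is why no size can be claimed.

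The drop-out allowance could be read to include deaths. That would cover their number but not their classification, and a rescued patient who has a CT is not a drop-out.

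The only later procedure with a stated frequency is endoscopic debridement, needed by more than half of patients according to the Background. A collection reduced that way also scores as a success. It can reasonably be treated as part of the assigned endoscopic strategy, but the plan should say so.

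Two stronger readings are tempting. A reader might take the Background sentence "Interventional approaches for management of symptomatic PFCs include endoscopic or surgical drainage" as evidence that the plan expects rescue. It compares first-line options and does not concern rescue after LAMS placement; only secondary endpoint 4 supports the point. A reader might also infer that the trial is underpowered or biased toward no difference. The documents give no rates from which either could be shown.

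**Conclusion.** The concern holds as a gap in outcome classification that should be fixed. On the text, rescue drainage before day 30 can turn a failure of the stent strategy into a primary success, and a death before the CT is unclassified. Secondary endpoint 4 shows that such procedures are expected and recorded, but it does not change the primary score.

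The size is unknown and the direction depends on which arm has more rescue. The movement from p=0.008 to p=0.08 rests wholly on assumed counts: four rescues with LAMS alone, none with the pigtail, 38 analysed per arm. The stated 80% power is reproduced and is not shown to be wrong. The study flow diagram is not reproduced in the text available, so a rule shown there cannot be excluded.

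**What to change.** These changes concern outcome classification only and leave clinical management untouched. They should be made before outcome data are seen by arm.

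1. In the primary endpoint, and identically in the failure definition of the power section, count surgical or percutaneous drainage of the collection, or death, before the day-30 CT (or by day 30 if no CT is done) as failure. Analyse by randomised arm.
2. State that endoscopic reintervention through the stent is treated as part of the assigned endoscopic strategy and stays under secondary endpoints 2 and 5.
3. Report the CT-only result as a sensitivity analysis, for comparability with the prior study.
4. Patients with one of these events are always counted, while event-free patients without a CT are not, which tilts failure rates upward. So also report a sensitivity analysis in all randomised patients with a missing CT counted as failure.
5. State that the 50% and 20% planning rates include these events. If deaths come on top of them, power at 38 per arm falls as shown in the last table.
6. Record the dates of surgical or percutaneous drainage and of death.

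The cost is a few sentences, two dates per affected patient and two extra analyses. If the planning rates are taken to include these events, the stated sample size does not change. There are two further downsides. The primary figure will no longer match the prior study exactly. The endpoint will also depend partly on a rescue decision made without blinding: the text describes none, and the endoscopist knows which stents were placed.

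### Does a collection that shrinks by exactly 50% fall between the primary endpoint and the failure definition?

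*Combined protocol and SAP*

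**What the plan says.** Under the heading for the primary endpoint, the protocol counts a patient as a success if there is a "Greater than 50% decrease in size of PFC (in mm), compared to pre-intervention size (in mm") on CT 30 days after stent placement. It gives a reason for the choice: consistency with an earlier multicentre study of these stents.

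The section on the power calculation and statistical analysis turns to failures. It makes an assumption about "the failure rate (<50% decrease in size of collection on 30 day imaging"), putting it at 50% for the metal stent alone and 20% for the metal stent plus pigtail. Taking alpha as 0.05 and power as 80%, it derives 38 patients per arm. The hypothesis to be rejected is "the null hypothesis that the failure rates for intervention A and B are equal". The section names the test in one further sentence: "Statistical analysis of this outcome will be performed using Chi square testing".

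Neither section mentions a decrease of exactly 50%, and neither says which wording takes precedence.

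**The concern.** The complement of a decrease greater than 50% is a decrease of 50% or less. The analysis section has a decrease of less than 50%. A patient whose collection halves exactly therefore misses the endpoint without being called a failure. The null hypothesis is stated on failure rates, and the chi-square sentence follows directly after them. A literal reader could thus build the 2x2 table from the narrower failure category, while a reader of the endpoint section would build it from those who missed the endpoint. The tables differ whenever there is an exact tie.

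Ties are possible because sizes are recorded in millimetres. If the coding were settled only after the data were seen, one patient could in principle decide a borderline primary result.

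**Working it through.** **1. The plan's own figure.** Inputs from the power section: failure rates p1 = 0.50 and p2 = 0.20, power 80%, alpha 0.05 (taken as two-sided; the plan does not say), 1:1 allocation.

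- Arcsine formula: n = 2(1.960 + 0.842)² / h², with h = 2·asin(√0.5) − 2·asin(√0.2) = 0.6435. This gives 37.9, so 38 per arm.
- Pooled normal formula: n = [1.960·√(2·0.35·0.65) + 0.842·√(0.25 + 0.16)]² / 0.30² = 38.5, so 39 per arm.
- Power at 38 per arm by the pooled formula: 79.5%.

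The stated 38 reproduces. Only the two rates enter the formula. The cut-off does not, so assigning ties to one side leaves 38 unchanged as long as 50% and 20% are the rates of the category analysed.

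**2. The two tables.**

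| 30-day result | Endpoint section | Power section |
|---|---|---|
| Decrease over 50% | endpoint met | not a failure |
| Decrease exactly 50% | endpoint not met | not a failure, read literally |
| Decrease under 50% | endpoint not met | failure |

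The sections differ only in the middle row.

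**3. How often the middle row is occupied.** The documents give no size distribution, so every input here except 38 per arm and the 50%/20% rates is an assumption. Follow-up size was simulated as baseline times a lognormal ratio, centred in each arm to give the planned failure rate. Both sizes were rounded to 1 mm and tested by uncorrected chi-square at 0.05.

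| Baseline mean (SD), mm | SD of log ratio | Expected ties in 76 | Chance of at least one | Codings disagree on significance |
|---|---|---|---|---|
| 60 (20) | 0.5 | 1.04 | 65% | 5.0% |
| 60 (20) | 1.0 | 0.52 | 41% | 2.9% |
| 100 (30) | 0.5 | 0.59 | 45% | 3.4% |
| 100 (30) | 1.0 | 0.30 | 26% | 1.8% |
| 150 (40) | 0.5 | 0.38 | 32% | 2.4% |
| 150 (40) | 1.0 | 0.19 | 17% | 1.3% |

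At 100 mm, power is 79.7% to 80.0% with ties left out of failures and 79.9% to 80.1% with ties counted as failures. Neither coding is favoured.

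A lognormal ratio never reaches zero, although the first secondary endpoint expects some collections to resolve completely. Suppose 30% (stent alone) and 50% (stent plus pigtail) had resolved by day 30, again an assumption, with the failure rates held. At 100 mm and log-SD 0.5, ties then fall from 0.59 to 0.39 and disagreement from 3.4% to 2.4%. The table therefore leans high.

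**4. What a tie does near the planned result.** Planned rates on 38 per arm give about 19 and 0.20 × 38 = 7.6, so 8, failures. Uncorrected chi-square:

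- 19 v 8: p = 0.008
- 19 v 9 (one tie added to the pigtail arm): p = 0.017
- 19 v 10 (two ties added): p = 0.034

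The conclusion holds with one or two ties recoded against the pigtail arm.

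**The case for a change.** The strongest case for a change is that the parenthesis in the power section is the only definition of failure in the documents, and it is attached to the quantity that is powered and tested. Close to the decision line one patient can matter: 18 v 9 failures gives p = 0.031, and 18 v 10 gives p = 0.057. A rule for that patient should exist before the data do, and supplying one costs a single symbol. In addition, if 1% to 5% of both arms sat at exactly 50% (an assumed range) and were added to failures on top of the planned rates, power at 38 per arm would be 78.9% to 77.2%.

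The textual point stands: the two inequalities are not complements, and no sentence ranks them. The rest carries less weight. The endpoint section is the formal, headed and justified definition. The other wording is a gloss inside a conditional sample-size assumption and is not offered as a second endpoint. To exploit the gap, an analyst would have to set the headed endpoint aside and score as a non-failure someone who did not meet it. The borderline example needs both a tie and a result on the line, which is the 1% to 5% of trials already counted. The lower power figures require ties to be extra to the assumed 50% and 20%. Those rates are round planning values, and a shift of one to three points is well inside their uncertainty.

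**Conclusion.** The wording slip is genuine, but following the plan gives a sound primary analysis, so no change is called for. The natural reading is that the endpoint section governs and that failure means not meeting it, which places an exact halving among the failures. Either coding, applied to both arms alike, is a valid comparison. The sample size is unaffected at 38 per arm, and power is about 80% both ways.

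Any effect on the result is confined to exact ties: about 0.2 to 1.0 expected in 76 patients, with the codings disagreeing in about 1% to 5% of trials. Those frequencies depend on assumed baseline sizes, an assumed spread of the size ratio and 1 mm readings; the documents support no firmer estimate. Confidence is high that the two phrases do not match, and equally high that the mismatch has little practical consequence.

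### The enrolment target of 101 does not follow from 76 subjects and 20% drop-out, which give 95; it matches about 25%

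*Combined protocol and SAP*

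**What the plan says.** The Power calculation and statistical analysis plan section assumes failure rates of 50% (LAMS alone) and 20% (LAMS plus double pigtail stent), 80% power, alpha 0.05, 1:1 allocation and a chi-square test. On that basis, "then 38 subjects will need to be enrolled in each intervention arm".

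The Study timeline section carries this forward. It opens with "In order to accrue 76 subjects (38 in each arm", and continues: "assuming a 20% drop-out rate, 101 total subjects would need to be enrolled in this study". It then forecasts that the target can be reached in 36 months.

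Drop-out is the only reason given for going from 76 to 101. The readable text states no other drop-out rate and no other enrolment total. The content of the study flow diagram is not visible in the copy reviewed.

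**The concern.** One sentence gives a base (76), a loss rate (20%) and a result (101), and the result does not follow from the other two. The enrolment total drives recruitment and the accrual forecast. The loss rate says how many subjects are expected to lack the 30-day CT on which the primary endpoint depends. As written, a reader can work out that 101 would absorb about 25% loss, but cannot tell whether 20% or 25% was expected. Someone who trusts the 20% might cut the target to 95 or 96. If 25% was the real expectation, that would leave the trial slightly short.

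**Working it through.** **Inputs.** From the power section: 38 per arm, failure rates 0.50 and 0.20, power 80%, alpha 0.05, 1:1 allocation, chi-square test. From the Study timeline section: 76 in total, 20% drop-out, 101 enrolled. The plan does not say whether alpha is one- or two-sided; two-sided is assumed here.

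**Step 1: the base of 38 per arm.** The pooled normal formula, with mean failure rate 0.35, is

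n = [1.96 × √(2 × 0.35 × 0.65) + 0.8416 × √(0.50 × 0.50 + 0.20 × 0.80)]² / 0.30² = 38.48 per arm.

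This rounds up to 39. The arcsine formula gives 37.9, which rounds up to 38. Power at 38 per arm is 79.5% by the pooled formula and 79.97% by exact enumeration of the uncorrected chi-square test. The base of 76 is therefore reasonable, and the fault is not there.

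**Step 2: inflation from 76 at 20%.**

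- Standard, N/(1 - d): 76/0.80 = 95.
- Rounded up per arm: 38/0.80 = 47.5, so 48 per arm, 96 in total.
- Simple mark-up, N × (1 + d): 76 × 1.2 = 91.2.
- Applied twice: 76 × 1.2² = 109.4; 76 × 1.2/0.80 = 114; 76/0.80² = 118.75.

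None gives 101, which is 6 above 95 and 5 above 96.

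**Step 3: the loss rate that 101 implies.** 1 - 76/101 = 24.8%. In the other direction, 76/0.75 = 101.3, which is 101 to the nearest whole number. Rounded up per arm, 38/0.75 = 50.67, so 51 per arm, 102 in total.

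**Step 4: could a different base explain it?** From 39 per arm, 20% loss gives 39/0.80 = 48.75, so 49 per arm, 98 in total; 25% gives 39/0.75 = 52 per arm, 104 in total. With a continuity correction the base is 45 per arm, and 90/0.80 = 112.5. To reach 101 at 20% the base would have to be about 101 × 0.80 = 80.8, but the sentence names 76.

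**Step 5: effect on power** (failure 50% v 20%, two-sided 0.05).

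| Enrolled | Loss | Evaluable | Per arm used | Exact power | Pooled formula |
|---|---|---|---|---|---|
| 101 | 20% | 80.8 | 40 | 81.7% | 81.6% |
| 101 | 25% | 75.75 | 38 | 80.0% | 79.5% |
| 96 | 25% | 72 | 36 | 78.7% | 77.2% |

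**The case against.** The arithmetic is not in dispute. The case on the other side is that it hardly matters, and most of that stands. The plan gives both the analysis target and the enrolment target, so the loss that 101 can absorb can be worked out; only the expected rate is unclear. Under either rate, 101 delivers roughly the planned power, and no analysis or estimate changes. The loss from enrolling 96 and losing 25% is also small: exact power falls by 80.0 - 78.7 = 1.3 percentage points (79.5 - 77.2 = 2.3 by the pooled formula), and the planned 38 per arm is itself marginally under 80%.

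A second argument is that 101 might cover losses before randomisation. The Methods section makes patients eligible to take part when they are "scheduled" in effect for drainage, and then says: "Adult patients with PFCs consisting of >30% solid component as assessed at the time of EUS will be eligible for randomization". Some participants might therefore never be randomised. Going from 95 to 101 would be 6 subjects, 6/101 = 5.9%. The text gives this little support. The Methods section treats the solid-component threshold as an enrolment criterion, and the power section speaks of subjects enrolled in each arm; both place enrolment after the EUS assessment. No such allowance appears in the readable text.

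The flow diagram cannot be read, so it could carry another figure. That would not make the Study timeline sentence consistent with itself.

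**Conclusion.** The concern holds, as a minor point. The stated pair of 20% drop-out and 101 enrolled is inconsistent: 20% requires 95 (96 with equal arms), and 101 implies 24.8%. The excess is 5 or 6 subjects and runs in the safe direction. Exact power with 101 enrolled is about 82% at 20% loss and about 80% at 25%, given the plan's failure rates, a two-sided 0.05 test and equal loss in the two arms. The validity of the primary analysis is not affected. The documents do not show which of the two figures is the error, and the match with 25% is suggestive only.

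**What to change.** The sponsor should establish which input was intended and restate the sentence in the Study timeline section so that the two figures agree:

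- **If about 25% was intended:** keep 101 and state that it absorbs about 25% loss, or use 102 for equal arms (51 × 0.75 = 38.25 per arm).
- **If 20% was intended:** state 96 (48 × 0.80 = 38.4 per arm).
- **If 101 also covers losses between consent and randomisation:** state that allowance separately from drop-out.

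Until this is confirmed, 101 is the safer figure to leave in place. The cost is one corrected sentence. If the total changes, the 36-month accrual forecast should be checked against the new figure. Lowering the target to 96 carries a small cost if loss turns out to be 25%: 72 evaluable subjects and exact power of about 79%.
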